1.3 Research Design and Methods

We will conduct a randomized clinical trial enrolling eligible participants who are determined to be SARS-CoV-2-positive (e.g., via Rutgers Corona Cohort [RCC] study, hospital or other screening programs) who volunteer for the study. Specifically, we will enroll 70 participants whose test has been performed within the past 7 days who are either asymptomatic or mildly symptomatic at baseline. Mild COVID-19 symptoms include new cough, sore throat, fever, myalgias, new vomiting or diarrheaor change in smell or taste. Illness requiring hospitalization, or those who present with hypoxia (PO2<92%) or shortness of breath at time of enrollment will be classified as significantly symptomatic and excluded from study participation. People who are allergic or intolerant to NTZ, RBV or HCQ will be excluded. We will randomly allocate participants stratified by presence of mild symptoms to 1) NTZ, RBV and HCQ or 2) placebo. Treatment with the investigational agents or placebo will continue for 5 days. Viral load will be assessed at baseline (day 0) as well as at days 3, 6, and 10 to monitor response to antiviral treatment. Immune status will be determined by antibody testing of blood collected at baseline and day 28.

Prior to initiating enrollment, we will prepare two randomization tables for treatment assignment using permuted blocks of six which will be provided to the research pharmacist. One table will be used for participants without symptoms and the other will be used for those with mild symptoms. The pharmacist will prepare kits containing the 5-day supply of study medications (investigational drugs/placebo) which will be sequentially numbered in accordance with the randomization tables. The contents of each kit (investigation drugs/placebo) will be indistinguishable. Study staff will establish symptom status at the baseline visit, and per pharmacy order, provide the participant the next numbered medication kit in the participant's stratum (no symptoms/mild symptoms). The study investigators, staff interacting with the participants are all masked to treatment assignment

A. Research Procedures

- 1. Study Procedures:
 - Day 0/1 Screening/Baseline Visit (in person)
 - Pre-screen via online screening form to confirm eligibility
 - Obtain informed consent for trial enrollment
 - Medical history
 - Medication history
 - Document symptoms (if any)

- o Take temperature, PO2, Pulse
- Q-T interval assessment
- Obtain urine pregnancy test for females of childbearing potential
- Collect research specimens: mid-turbinate nasal swab and blood for CBC, chem profile and immune status
- Randomize study participant
- Dispense study medication
- Provide Zio AT ECG monitoring device for ongoing Q-T interval assessment
- Provide thermometer and pulse oximeter and home collection kits and provide education on use
- Provide education to participant on how to complete temperature log and confirm medication self-dosing and self-collection of mid-turbinate swab.
- Study participant doses self with prescribed study medications the same day if instructed by the study staff

• Days 1-5 – Treatment Period (phone /online)

- Study participant doses self with prescribed study medications days 1 to 5
- Self-collecting of mid-turbinate swab day 3
- Questionnaire completed by participant daily day 1-day 5
- Temperature, PO2, and pulse
- o Day 3 telephone call procedure review and confirm self- specimen collection/AEs
- Days 6- 10
 - Questionnaire completed by participant days 6 to10
 - Self-collecting of mid-turbinate swab days 6 and 10
 - Temperature, PO2 and pulse
 - Day 6 and 10 telephone call procedure review and confirm self-specimen collection/AEs
- Day 14- Follow-up (in person)
 - In person visit to draw blood sample for CBC and chem panel
 - o Return Zio AT ECG monitoring device
- Day 28 Follow-up (in person)
 - In person visit to draw blood sample for CBC, chem panel, and immune function at 28 days
 - Obtain urine pregnancy test for females of childbearing potential
 - o Questionnaire completed by participant
 - o Final AE assessment

Study Flow/Schedule of Events:

Procedure	Pre- Screen -5 days	Screening /Baseline (Day 0/1)	Daily x 5 days	Days 6 to 10	Days 3, 6, 10	Day 14 (Office)	Day 28 +/- 4 (Office)
Pre-screen questionnaire	Х						
Consent		Х					
Baseline questionnaire (inc. Medical History)		X					
Q-T Interval		Х	Х	Х			
Self administered Symptom questionnaire		Х	Х	X			Х
Drug accountability (Treatment compliance)		Х	Х				X
Temperature		Х	Х	х			
PO2 and Pulse		Х	Х	х			
Urine Pregnancy Test		Х					Х
CBC w/ diff/platelet		Х				Х	Х
Comprehensive metabolic panel		Х				Х	Х
Mid-turbinate self nasal swab for viral shedding		Х			Х		
Blood test for immune function		X					Х
Study medication		X (if day1)	X (BID)				
Telephone Follow-up procedure review & confirm self- specimen collection/					X		
AE Review					х		x

- 2. Treatment Plan:
 - Dosage and Administration
 - Arm 1: NTZ 1000 mg (2 x 250 mg tablets BID for day one) and then 1000 mg (2 x 250 mg tablets BID for 4 days) RBV 1200 mg (3 x 200 mg capsules BID day one) and then RBV 800 mg (2 x 200mg capsules BID for 4 days) HCQ 800 mg (2 x 200 mg tablets bid day one) and then HCQ 400 mg (1 x 200 mg tablet BID for 4 days)
 - Arm 2: Placebo for NTZ (2 tablets BID for day one and then 2 tablets BID for 4 days) Placebo for RBV (3 capsules BID day one and then 2 capsules BID for 4 days) Placebo for HCQ (2 tablets bid day one and then 1 tablet BID for 4 days)

Hydroxychloroquine sulfate (HCQ)

One hydroxychloroquine sulfate tablet contains 200 mg of hydroxychloroquine sulfate, which is the equivalent to 155 mg base.

Ribavirin (RBV)

One ribavirin capsule contains 200 mg of ribavirin.

Nitazoxanide (NTZ)

One nitazoxanide tablet contains 500 mg of nitazoxanide.

Take all tablets/capsules with a meal or a glass of milk.

All study drugs should be stored at room temperature 20°-25° (68°-77 °F).

Concomitant Medications & Supportive Guidelines

Study participants can receive full supportive care therapies concomitantly during the study. We will advise rest, fluids, hot/ showers/baths. We will recommend NO antipyretics since they make infections worse by interfering with the generation of fever--which is considered beneficial until it reaches 102 degrees F.

B. Participant Enrollment

We will identify asymptomatic or mildly symptomatic participants who test positive for SARS-CoV-2 from the Rutgers Coronavirus Cohort (RCC) and hospital screening programs, or from the community through advertisements at our medical center, university, and in local publications. The recruiting materials will direct the potential participants to online materials that include information about the trial, consent forms, and a screener questionnaire to assess eligibility. If eligible for the trial, we will answer any questions and provide as much time as needed to review all study materials. The participant may then electronically sign the consent or, as an alternative, wait until the initial visit to re-review and sign the consent. The consenting process will be primarily performed remotely to protect research personnel.

As soon as possible after consent, the participant will participate in an in person visit for baseline biospecimen collection. On arrival, research staff wearing PPE will re-review the consent, confirm/obtain signatures, measure the PO2, do a urine pregnancy test in women with potential to be pregnant and measure the baseline QTc interval with the Kardia Mobile 6L (AliveCor, Inc). A 6 lead EKG is obtained when the patient places their fingers on 2 electrode sensors while holding

the device on their leg. The ECG is uploaded to an iPhone and the tracing is sent to the Electrophysiologist cardiologist who will calculate the QT and QTc. The device is approved by the FDA for QTc measurements. The participant will be excluded if the Q-T interval is prolonged beyond 450 Msec. We will also exclude anyone who has a PO2<92% or a positive pregnancy test. We will randomly allocate the participant, provide the assigned medications, and obtain mid-turbinate self nasal swab and blood samples. We will also take the participant's temperature and pulse. We will provide education to the patient on how to complete all at-home study procedures and use all ancillary study supplies which we will provide (self nasal swab specimen kits, thermometer, and pulse oximeter).

We will telephone the participant about 2 hours after the initial medication dose to confirm that the Zio AT patch has been triggered for the one-time 2 hour reading (see the Risks of Harm/Potential for Benefits to Subjects to Subjects section, page 35), review the BID dosing schedule, study procedures, and any participant questions. We will also call on days 3, 6, and 10 for procedure review and to confirm self- specimen collection and AE review. We will have an in person visit on day 14 to collect a blood specimen and on day 28 to collect a blood specimen and urine pregnancy test, review medical status and AEs Self collection of mid-turbinate nasal swab to measure viral shedding will be on days 3, 6 and10 post randomization.

QT interval will be measured on an ongoing basis through day 10 via the Zio AT mobile cardiac telemetry device describe in section 4.7 E. If the corrected QT - QTc interval increases from baseline of > 60msec or QT > 500 msec, the medications, if still being taken, will discontinued at that time. Participant QTc intervals will be monitored every 6 hours until the interval returns to baseline. If a serous arrhythmia is detected during the continuous monitoring, the study cardiologist and participant will be promptly contacted, and the participant will be directed to seek medical treatment as appropriate.

C. Study Safety Assessments

The Principal Investigator is responsible for ensuring that all staff involved in the study are familiar with the content of this section.

- 1. Definitions:
 - Adverse Events:

An adverse event is the development of an undesirable medical condition or the deterioration of a pre-existing medical condition following or during exposure to a pharmaceutical product, whether considered causally related to the product. An undesirable medical condition can be symptoms (e.g., nausea, chest pain), signs (e.g., tachycardia, enlarged liver), or the abnormal results of an investigation (e.g., laboratory findings, electrocardiogram). In clinical studies, an AE can include an undesirable medical condition occurring at any time, including run-in or washout periods, even if no study treatment has been administered. The term AE is used to include both serious and non-serious AEs.

• Serious Adverse Events:

A serious adverse event is an AE occurring during any study phase (i.e., screening, runin, treatment, wash-out, follow-up), at any dose of the study drugs that fulfills one or more of the following criteria:

- Results in death
- Is immediately life-threatening
- Requires in-patient hospitalization or prolongation of existing hospitalization
- Results in persistent or significant disability or incapacity

- Is a congenital abnormality or birth defect
- Is an important medical event that may jeopardize the patient or may require medical intervention to prevent one of the outcomes listed above.
- The causality of SAEs (their relationship to all study treatment/procedures) will be assessed by the investigator(s) and communicated to the FDA via MedWatch form, if applicable.
- 2. Recording of Adverse Events

Non-serious adverse events and SAEs will be determined from the time the study drug is given, throughout the treatment period and up to and including the one month follow-up period. All grade 3 or higher AEs will be recorded. Grade 1 - 2 AEs do not need to be recorded. After withdrawal from treatment, participants must be followed-up for all existing and new AEs for 60 calendar days after the last dose of trial drug and/or until event resolution. All new AEs occurring during that period must be recorded (if SAEs, they must be reported to Data Safety Monitoring Board (DSMB) and Rutgers IRB as per SOPs.).

All study-related toxicities/ SAEs must be followed until resolution, unless in the Treating Investigator's opinion, the condition is unlikely to resolve due to the patient's underlying disease.

3. Reporting of Serious Adverse Events

Investigators and other site personnel must inform the DSMB and Rutgers IRB. FDA will be informed as required accordance with the reporting obligations of 21 CFR 312.32. It is the responsibility of the principal investigator to compile all necessary information and ensure that the FDA receives a report according to the FDA reporting requirement timelines.

All SAEs meeting the criteria for expedited reporting will be reported to the Rutgers IRB within the mandated time frames. All SAEs within the safety follow-up window (e.g., within 30 days after the last dose of study medications) established in the protocol will be reported.

- 4. Clinical Safety Assessments
 - Recording of Adverse Events

Non-serious adverse events and SAEs will be determined from the time the study drug is given, throughout the treatment period and up to and including the 28-day follow-up period. All grade 3 or higher AEs will be recorded. Grade 1-2 AEs do not need to be recorded. After withdrawal from treatment, participants must be followed-up for all existing and new AEs for 28 calendar days after the last dose of trial drug and/or until event resolution. All new AEs occurring during that period must be recorded (if SAEs, they must be reported to the Data Safety Monitoring Committee and Rutgers IRB).

 Adverse Events Based on Signs and Symptoms When collecting AEs, the recording of diagnoses is preferred (when possible) to recording a list of signs and symptoms. However, if a diagnosis is known and there are other signs or symptoms that are not generally part of the diagnosis, the diagnosis and each sign or symptom will be recorded separately.

D. Data Points

Case Report Forms

Completion of the electronic case report forms (eCRFs) will be done in accordance with the instructions outlined in the study specific data capture plan. All eCRFs are considered the primary

data collection document for the study and are stored in REDCap in a confidential format. Only key personnel who are delegated in the delegation of authority log are permitted to make entries, changes, or corrections in the eCRF. All users will complete user training, as required or appropriate per regulations. An audit trail will be maintained automatically by the electronic CRF management system.

Data Points to be collected:

- Baseline medical history
- Treatment compliance
- Daily temperatures
- Symptoms of disease
- Adverse events
- Concomitant medications
- Any standard of care treatments or procedures to manage COVID-19
- Viral load from saliva specimen
- Viral load from mid-turbinate self-nasal swab
- SARS-CoV-2 infections confirmed or suspected in household members

Data Submission Timeline and Forms

Completion of eCRFs will occur within 72 hours of study time point unless otherwise indicated. Baseline (pre-study) eCRFs (e.g., enrollment, medical history, concomitant medications, etc.) will be completed no later than 24 hours after the start of treatment.

E. Study Duration

Study participants will be treated for five (5) days and will then remain on follow-up for up to 28 days after entry into the study. The estimated time to complete the entire study including data analysis is 3-6 months

F. Endpoints

Primary endpoint:

1. Rate of decline in viral load over the 10 days after randomization

Secondary:

- 1. Proportion of participants with virus below LLOQ at day 10
- 2. Proportion of participants asymptomatic at day 10.
- For those who were asymptomatic at baseline: Progression to symptoms--presence or absence of key symptoms: fever ≥ 100.4^o F (38 ^o C); sore throat, cough, shortness of breath, myalgias, vomiting or diarrhea, or change in smell or taste
- 4. Proportion of participants with progression of severity of COVID-19 symptoms (hospitalization and length of stay; admission to intensive care unit and number of days in unit; Intubation; Death (any cause))
- 5. Comparison of severity of disease in participants who develop symptoms of COVID-19 at all timepoints
- 6. Assessment of medication toxicity as measured by standard metrics
- 7. Q-T interval from baseline of > 60msec or QT > 500 msec)
- 8. Number of participants with undetectable viral load and absence of symptoms
- 9. Rate of decline in viral load at study days 3 and 6
- 10. New, self-reported COVID infection in household members

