During combination therapy for up to 48 weeks with peginterferon alfa-2a plus ribavirin, growth inhibition was observed in pediatric participants 5 to 17 years of age. Decreases in weight for age z-score and height for age z-score up to 48 weeks of therapy compared with baseline were observed. At 2years post-treatment, 16% of pediatric participants were more than 15 percentiles below their baseline weight curve and 11% were more than 15 percentiles below their baseline height curve. The available longer term data on participants who were followed up to 6 years post-treatment are too limited to determine the risk of reduced adult height in some patients [see Clinical Studies Experience

Drug interactions: Didanosine, zidovudine

Availability: FDA approved; commercially available Ribavirin will be supplied free of charge to all patients enrolled.

[figure not shown]
Generic name: Nitazoxanide Commercial name: ALINIA

For complete information please refer to the package inserts at http://dailymed.nlm.nih.gov/dailymed/nitazoxanide

Chemical name: 2-acetyloxy- N-(5-nitro-2-thiazolyl) benzamide

Source: Commercially available

 C_{12} H₉ N₃ O₅ S and the molecular weight is 307.3

Nitazoxanide is a light yellow crystalline powder. It is poorly soluble in ethanol and practically insoluble in water.

ALINIA Tablets contain 500 mg of nitazoxanide and the following inactive ingredients: maize starch, pregelatinized corn starch, hydroxypropyl methylcellulose, sucrose, sodium starch glycollate, talc, magnesium stearate, soy lecithin, polyvinyl alcohol, xanthan gum, titanium dioxide, D&C Yellow No. 10 Aluminum Lake, FD&C Yellow No. 6 Aluminum Lake, and FD&C Blue No. 2 Aluminum Lake.

ALINIA for Oral Suspension, when reconstituted with 48 mL of water, produces 60 mL of a homogeneous suspension with a pink color that contains 100 mg nitazoxanide per 5 mL and the following inactive ingredients: sodium benzoate, sucrose, xanthan gum, microcrystalline cellulose and carboxymethylcellulose sodium, anhydrous citric acid, sodium citrate dihydrate, maltodextrin, modified food starch, triacetin, FD&C Red No. 40 and artificial strawberry flavoring.

Pharmacokinetics

Absorption Single Dosing: Following oral administration of ALINIA Tablets or Oral Suspension, the parent drug, nitazoxanide, is not detected in plasma.

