Multiple dosing: Following oral administration of a single ALINIA Tablet every 12 hours for 7 consecutive days, there was no significant accumulation of nitazoxanide metabolites tizoxanide or tizoxanide glucuronide detected in plasma.

Bioavailability: ALINIA for Oral Suspension is not bioequivalent to ALINIA Tablets. The relative bioavailability of the suspension compared to the tablet was 70%. When ALINIA Tablets are administered with food, the AUC of tizoxanide and tizoxanide glucuronide in plasma is increased almost two-fold and the C_{max} is increased by almost 50%. When ALINIA for Oral Suspension was administered with food, the AUC of tizoxanide glucuronide increased by about 45-50% and the C_{max} increased by $\leq 10\%$.

Distribution: In plasma, more than 99% of tizoxanide is bound to proteins.

Elimination Metabolism: Following oral administration in humans, nitazoxanide is rapidly hydrolyzed to an active metabolite, tizoxanide (desacetyl-nitazoxanide). Tizoxanide then undergoes conjugation, primarily by glucuronidation.

Excretion: Tizoxanide is excreted in the urine, bile, and feces, and tizoxanide glucuronide is excreted in urine and bile. Approximately two-thirds of the oral dose of nitazoxanide is excreted in the feces and one-third in the urine.

Contraindications:

Hypersensitivity: ALINIA Tablets and ALINIA for Oral Suspension are contraindicated in patients with a prior hypersensitivity to nitazoxanide or any other ingredient in the formulations.

Drug interactions: Highly Protein Bound Drugs with Narrow Therapeutic Indices i.e. Tizoxanide, warfarin

Availability: FDA approved; commercially available Ribavirin will be supplied free of charge to all patients enrolled.

There is no current data that assess the risks of the use of all three drugs in combination.

A. Drug/Device Accountability and Storage Methods

Drug accountability logs and pharmacy records must be maintained at each pharmacy location and must be available for review upon request. Drug accountability logs and pharmacy records will be reviewed during monitoring visits and by the Research Pharmacist

B. Treatment Compliance

The study medication will be given in accordance with the protocol and the instructions of the treating investigator. The study drugs will be provided to participants to be self-administered. Participants will be asked to confirm medication dosing each day on daily logs and on the day 3 and day 6 call with research staff.

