During combination therapy for up to 48 weeks with peginterferon alfa-2a plus Ribavirin, growth inhibition was observed in pediatric participants 5 to 17 years of age. Decreases in weight for age z-score and height for age z-score up to 48 weeks of therapy compared with baseline were observed. At 2 years post-treatment, 16% of pediatric participants were more than 15 percentiles below their baseline weight curve and 11% were more than 15 percentiles below their baseline height curve.

The available longer term data on participants who were followed up to 6 years post-treatment are too limited to determine the risk of reduced adult height in some patients.

NITAZOXANIDE Adverse Events

Gastrointestinal

Gastrointestinal side effects have included abdominal pain (6.6% to 7.8%), diarrhea (2.1% to 4.2%), and nausea (3%). Side effects occurring in less than 1% of patients have included vomiting, anorexia, flatulence, dyspepsia, constipation, dry mouth, and thirst.

The incidence of gastrointestinal side effects may be dose related. Abdominal pain, diarrhea and discolored urine occurred more often in participants receiving higher doses (1 gram twice daily).

Nervous system

Nervous system side effects have included headache (3.1%). Dizziness, somnolence, insomnia, tremor, and hypesthesia have been reported by less than 1% of the patients.

Other

Adverse effects affecting the body as a whole have included asthenia, fever, pain (pelvic/back), flu syndrome, earache, and chills in less than 1% of patients.

Metabolic

Metabolic side effects have included increased creatinine and SGPT in less than 1% of patients.

Dermatologic

Dermatologic side effects have included pruritus, rash, and sweat in less than 1% of patients.

Ocular

Ocular side effects have included pale yellow eye discoloration (<1%).

Respiratory

Respiratory side effects have included epistaxis, rhinitis, lung disease, and pharyngitis.

Genitourinary

Genitourinary side effects have included discolored urine, dysuria, amenorrhea, metrorrhagia, and edema labia.

General

In general, side effects have been mild and transient in nature. The most frequent side effects have included abdominal pain, diarrhea, vomiting, and headache, and the rates of occurrence were not significantly different from placebo.

Musculoskeletal

Musculoskeletal side effects have included myalgia, leg cramps, and spontaneous bone fracture.

Cardiovascular

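### The nitazoxanide tablet is 250 mg in the Arm 1 dosing line but 500 mg in the product line of the same section, so the tablet count that delivers 1000 mg/day is not settled

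*Combined protocol and SAP*

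**What the plan says.** Section 1.3, A.2 (Treatment Plan, Dosage and Administration) specifies nitazoxanide in three places:

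- **Arm 1, active:** "NTZ 1000 mg (2 x 250 mg tablets BID for day one". The same daily total, strength and count follow for the remaining four days.
- **Arm 2, placebo:** "Placebo for NTZ (2 tablets BID for day one and then 2 tablets BID for 4 days".
- **Product line:** "One nitazoxanide tablet contains 500 mg of nitazoxanide".

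The drug description in section 1.7 mentions only one tablet strength: "ALINIA Tablets contain 500 mg of nitazoxanide and the following inactive ingredients". It gives the source as commercially available.

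On handling, section 1.3 states: "The pharmacist will prepare kits containing the 5-day supply of study medications". Section 1.7 B adds: "The study drugs will be provided to participants to be self-administered". Section 1.7 A provides a check: "Drug accountability logs and pharmacy records will be reviewed during monitoring visits and by the Research Pharmacist".

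**The concern.** A dosing instruction needs a strength, a count and a frequency that multiply to the intended dose. Here the strength has two values in the current text of one section. The documents mention no 250 mg nitazoxanide product, tablet splitting or over-encapsulation that would explain the difference.

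Participants take blinded medication at home by counting tablets, so the count determines the dose. If 500 mg tablets were packed at the written count, the active arm would take 1 g twice daily. Section 4.7 A comments on that level: "Abdominal pain, diarrhea and discolored urine occurred more often in participants receiving higher doses (1 gram twice daily". Three further points bear on that case:

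- Diarrhea is one of the symptoms that define progression in participants asymptomatic at baseline (section 1.3 F, secondary endpoint 3). Extra drug-related diarrhea in the active arm could therefore affect an efficacy endpoint as well as tolerability.
- Section 1.3 C does not require grade 1–2 adverse events to be recorded, so a mild gastrointestinal excess might not appear in the adverse event data.
- Compliance rests on participants confirming their own dosing. Someone following the written count would look fully compliant at either strength.

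The protocol also states (sections 1.4 and 1.7) that there is no earlier human experience with the triple combination and no data on its risks, which is a further reason for the dose to be certain.

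**Working it through.** **Inputs**, all from section 1.3 A.2 except the last:

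- Nitazoxanide, Arm 1: 1000 mg; 2 tablets of 250 mg per dose, two doses a day, on all 5 days (1 + 4).
- Nitazoxanide product line: 500 mg per tablet.
- Nitazoxanide placebo: 2 tablets per dose, two doses a day, on all 5 days.
- Ribavirin: 1200 mg as 3 × 200 mg twice daily on day one, then 800 mg as 2 × 200 mg twice daily.
- Hydroxychloroquine: 800 mg as 2 × 200 mg twice daily on day one, then 400 mg as 1 × 200 mg twice daily.
- Participants per arm: 35 (section 1.5).

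**Formula:** daily dose = tablets per dose × mg per tablet × 2 doses per day.

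**Step 1. Are the headline mg figures daily totals?** The other two drugs settle this.

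- Ribavirin: 3 × 200 × 2 = 1200 and 2 × 200 × 2 = 800.
- Hydroxychloroquine: 2 × 200 × 2 = 800 and 1 × 200 × 2 = 400.

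All four match, so the headline figures are daily totals. For both drugs the 200 mg in the arm line also agrees with the product line in section 1.3. Within that section, the conflict is confined to nitazoxanide.

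**Step 2. Reproduce the plan's nitazoxanide figure.** With the Arm 1 strength, 2 × 250 × 2 = 1000 mg/day, as stated.

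**Step 3. Try each strength with each count.**

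| Tablet | Count per dose | mg/day | Total over 5 days | Tablets per kit |
|---|---|---|---|---|
| 250 mg | 2 (as written) | 2 × 250 × 2 = 1000 | 5 g | 2 × 2 × 5 = 20 |
| 500 mg | 2 (as written) | 2 × 500 × 2 = 2000 | 10 g | 20 |
| 500 mg | 1 | 1 × 500 × 2 = 1000 | 5 g | 1 × 2 × 5 = 10 |
| 250 mg | 1 | 1 × 250 × 2 = 500 | 2.5 g | 10 |

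The written count with the product-line strength gives 2000 / 1000 = 2 times the intended dose. The last row shows that the opposite mistake is also possible: changing the count to one without checking the strength could halve the dose.

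**Step 4. Supply.** At 1000 mg/day, each arm needs 20 × 35 = 700 tablets of 250 mg or 10 × 35 = 350 of 500 mg, with the same number of placebo tablets in Arm 2. This matters for kit preparation; it does not measure harm.

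**The case against.** The strongest reply is that the operative instruction is complete and consistent in itself. Two tablets twice daily is written four times, across both arms and both dosing periods. With the stated 250 mg it gives exactly the stated 1000 mg. On this view a single descriptive sentence is wrong and the count is not in doubt.

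Section 1.7 is also weak evidence for 500 mg. It is label text and does not track the trial supply closely: it describes ribavirin as a tablet in several strengths although the trial uses 200 mg capsules, covers a nitazoxanide oral suspension that the trial does not use, and names ribavirin in the availability line for nitazoxanide.

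A double dose would need 500 mg tablets to be supplied and the pharmacist to pack two per dose despite an order reading 250 mg and 1000 mg. Kit preparation and the review of pharmacy records give chances to notice. Section 4.7 A describes nitazoxanide side effects as generally mild and transient, with the commonest occurring at rates not significantly different from placebo, although that statement is not tied to the 1 g dose.

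Much of this stands. The daily dose is unambiguous, section 1.7 supports the 500 mg reading without proving it, and an overdose is not shown. What does not follow is that the count is settled. Two tablets twice daily delivers 1000 mg only if the tablet is 250 mg, and that strength is exactly what the same section contradicts. A pharmacist who noticed the mismatch would still have to choose between two protocol statements, and the checks would not correct the text.

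**Conclusion.** The concern holds. Section 1.3 A.2 gives two strengths for the same tablet, and one of them must be wrong. The potential dose error is a factor of two (2000 against 1000 mg/day) if 500 mg tablets are packed at the written count, and zero if 250 mg tablets are supplied. The documents do not establish which applies. The conclusion relies on reading 1000 mg as a daily total, which the ribavirin and hydroxychloroquine lines confirm. Because this is a core dosing instruction for self-administered, blinded medication, it must be corrected before dispensing even though the harm is conditional.

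**What to change.** Confirm with the research pharmacy which strength is supplied, keep 1000 mg/day, and make one of two edits:

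1. **If 500 mg tablets are supplied:** change Arm 1 to one 500 mg tablet twice daily on all five days and the nitazoxanide placebo to one tablet twice daily (10 tablets per kit).
2. **If 250 mg tablets are supplied:** keep two tablets twice daily in both arms (20 per kit), correct the product line in section 1.3 A.2 to 250 mg, and describe the 250 mg product in section 1.7.

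Confirmation must come first, because applying the first edit to 250 mg tablets would give only 500 mg/day. The active and placebo counts must stay the same to preserve the blind. Carry the correction into the kit instructions and accountability forms, and verify the strength in any kits already made.

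The cost is a few lines of wording and a pharmacy check, with no change to sample size, power or analysis.
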